7.1.1.2. DRUG – ADVERSE EVENT RELATIONSHIP

Relationship of the AE to the treatment will be assessed by the investigator as either: **Yes or No**

If there is a reasonable suspected causal relationship to the study medication, i.e., there are facts (evidence) or arguments to suggest a causal relationship, drug-event relationship should be assessed as **Yes**. The following criteria should be considered in order to assess the relationship as **Yes**:

- Reasonable temporal association with drug administration.
- May or may not have been produced by the patient's clinical state, environmental or toxic factors, or other modes of therapy administered to the patient
- Known response pattern to suspected drug
- Disappears or decreases on cessation

The following criteria should be considered in order to assess the relationship as **No**:

- It does not follow a reasonable temporal sequence from the administration of the drug.
- It may readily have been produced by the patient's clinical state, environmental or toxic factors, or other modes of therapy administered to the patient.

- It does not follow a known pattern of response to the suspected drug.

7.1.1.3 SERIOUS ADVERSE EVENTS

An SAE is any experience that suggests a significant hazard, contraindication, side effect or precaution. It is any AE that at any dose fulfills at least one of the seriousness criteria following criteria:

- is fatal/results in death (**NOTE:** death is an outcome, not an event)
- is life-threatening (i.e. refers to an event in which the patient was at immediate risk of death at the time of the event; it does not refer to an event which could hypothetically have caused a death had it been more severe).
- requires in-patient hospitalization or prolongation of existing hospitalization;
- results in persistent or significant disability/incapacity;
- is a congenital anomaly/birth defect;
- is medically significant or requires intervention to prevent one or other of the outcomes listed above.

SAE reporting procedures are described in [Section 7.2](#). Death is the outcome of an event and will not be reported as the SAE term, rather the event causing the death will be reported as the SAE. The only exception is when the cause of death is not known; these cases will be reported as “Death Unknown”.

7.1.2 LABORATORY TEST ABNORMALITIES

Any laboratory result abnormality fulfilling the criteria for a SAE will be reported as such, in addition to being recorded as an AE in the study record.

Any treatment-emergent abnormal laboratory result which is clinically significant, i.e., meeting one or more of the following conditions, will be recorded as a single diagnosis in the study record:

- Accompanied by clinical symptoms
- Leading to a change in study medication (e.g., interruption or permanent discontinuation)
- Requiring a change in concomitant therapy (e.g., addition of, interruption of, discontinuation of, or any other change in a concomitant medication, therapy or treatment).

This will apply to any protocol and non-protocol specified safety and efficacy laboratory result from tests performed after the first dose of study medication, which falls outside the laboratory reference range and meets the clinical significance criteria.

This will not apply to any abnormal laboratory result which falls outside the laboratory reference range but which does not meet the clinical significance criteria, or those which are a result of an AE which has already been reported.

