7.1.1.1 INTENSITY

All clinical AEs encountered during the clinical study will be reported in the study record. The intensity of AEs will be graded by the investigator on a three-point scale (mild, moderate, severe) and reported in detail on the CRF.

| | |
|----------|---|
| Mild | discomfort noticed but no disruption of normal daily activity |
| Moderate | discomfort sufficient to reduce or affect daily activity |
| Severe | inability to work or perform normal daily activity |

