7.1.3 TREATMENT AND FOLLOW UP OF AEs

AEs will be followed up until they have returned to baseline status or stabilized. Details of follow up will be recorded in the study record including if return to baseline status or stabilization cannot be achieved.

In the event of medically significant unexplained abnormal laboratory test values, the tests will be repeated and followed up until they have returned to the normal range or the baseline value and/or an adequate explanation of the abnormality is found. All details will be included in the study record.

If the study drug is discontinued due to an AE or a laboratory abnormality, the study medication will not be reinstated. If the investigator decides to discontinue study drug treatment, the rationale for their decision will be provided in the AE comment/SAE narrative field of the study record.

Study drug will be discontinued in the presence of an SAE that is deemed to be related or possibly related. Thromboembolic events or any event which a participant finds intolerable, which cannot be mitigated with therapy, will be cause for VOR discontinuation. Participants experiencing a $\geq 50\%$ increase in seizure frequency, as compared to baseline at any time during the treatment period will be discontinued from study medication. Additionally, participants presenting with status epilepticus at any time during the treatment period will be discontinued from study medication.

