Treatment with VOR is associated with dose-related hematologic adverse effects⁴⁰. Participants will be monitored as per laboratory testing schedule to identify such disturbances. Additionally participants will be advised to contact the investigator if presenting with frequent bruising, nose bleeds or gum bleeding, blood in urine or stools, or petechiae.

QT/QTc Prolongation

Treatment with VOR is associated with QT/QTc interval prolongation⁴⁰, which is suspected to increase the risk of Torsade de pointes. Torsade de pointes may be asymptomatic or may be experienced as dizziness, palpitations, syncope, or increased seizures. Participants will be instructed to contact the investigator if presenting with these symptoms. Additional ECG monitoring may be conducted.

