8.1 PRIMARY AND SECONDARY STUDY ENDPOINTS

8.1.1 PRIMARY ENDPOINTS

The primary endpoint for this study will be the incidence of related AEs and SAEs, and discontinuation of therapy due to intolerable AEs.

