8.2.2 ANALYSIS

8.2.2.1. SAFETY & TOLERABILITY ANALYSIS

Safety and tolerability will be assessed by calculating the incidence rate of AEs per number of drug days from the time medication is started through to the completion of the SFU (or 42 days following the last dose of study medication). This will be done for the following time points: 14 days following drug initiation; 30 days following drug initiation; 42 days following drug initiation; and 42 days following drug discontinuation. AEs will be further stratified by mild/moderate AEs, severe AEs, and SAEs, as well as project specific AEs (thromboembolism, hyperglycemia, gastrointestinal disturbances, dehydration, hematologic disturbances, QT/QTc prolongation).

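### Whether a symptom-free fall in blood counts is counted as an AE depends on which AE definition the investigator follows, and Section 8 plans no laboratory summary that would show what is left out.

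*Combined protocol and SAP*

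**What the plan says.** Section 7.1.2 sets the recording rule for laboratory results. A result that meets an SAE criterion is reported as an SAE and recorded as an AE. A treatment-emergent result counts as clinically significant, and must be recorded as a diagnosis, if it comes with symptoms, leads to a change in study medication, or requires a change in concomitant therapy. For the remainder: "This will not apply to any abnormal laboratory result which falls outside the laboratory reference range but which does not meet the clinical significance criteria".

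Other sections bear on the same results:

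- Section 7.1.1 includes abnormal laboratory findings in its AE definition, if unfavourable and unintended, without the three conditions of 7.1.2.
- Section 5.3.1 includes laboratory abnormalities that are clinically relevant. It does not define that term or tie it to 7.1.2.
- Section 7.1.1.3 makes an event serious if, among other criteria, it "is medically significant or requires intervention to prevent one or other of the outcomes listed above". No count threshold is given.
- Section 7.1.3 adds: "In the event of medically significant unexplained abnormal laboratory test values, the tests will be repeated and followed up". Details go into the study record.
- Section 7.1.3.1 says of hematologic effects: "Participants will be monitored as per laboratory testing schedule to identify such disturbances".

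The planned safety analysis in 8.2.2.1 consists of "calculating the incidence rate of AEs per number of drug days from the time medication is started". It continues: "AEs will be further stratified by mild/moderate AEs, severe AEs, and SAEs, as well as project specific AEs". Hematologic disturbances are one of the six project-specific classes. The primary endpoint in 8.1.1 is "the incidence of related AEs and SAEs, and discontinuation of therapy due to intolerable AEs". Nothing in Section 8 summarises laboratory values.

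**The concern.** Section 1.1.4.3 expects a higher proportion of hematologic events than with other anti-seizure drugs and gives this as a reason for blood tests every two weeks. What such tests can add to clinical observation is mainly the detection of changes that cause no symptoms. These are the results that 7.1.2 takes out of required recording when nobody acts on them and nobody judges them serious.

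If an investigator works from 7.1.2, those results do not become AEs and so do not reach the hematologic class. If the investigator works from 7.1.1, they may. The reported rate then reflects recording practice as well as the drug. Omission under 7.1.2 can only lower the class rate. A result that would have been judged related is also lost from the primary endpoint. Because 8.2.2.1 has no laboratory table, a reader of the results could not tell whether the class was low because counts were stable or because changes were not recorded.

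**Working it through.** The plan states no figure for this point; 8.2.1 says that no power-based sample size could be calculated. The main check is to follow one result through the sections.

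**One result, several rules.** Take a platelet count below the reference range at week 4, with no symptoms, no change in study drug or other therapy, and no judgement that it is medically significant.

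1. Under 7.1.1 it is an abnormal laboratory finding. If seen as unfavourable and unintended it is an AE, 7.2.1 has new AEs recorded, and 8.2.2.1 counts it.
2. Under 5.3.1 it is an AE only if clinically relevant, which is left to judgement.
3. Under 7.1.2 it meets none of the three conditions and no SAE criterion. Recording is not required, and 8.2.2.1 would not count it.
4. The follow-up rule in 7.1.3 applies only to values that are medically significant and unexplained. Where it applies, the details are documented, but the section does not make them AEs or send them to an analysis.

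The same blood count therefore contributes either one event or none to the hematologic class. No section says which rule governs.

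**What one event is worth on the planned scale.** Inputs: 12 participants (3.3), and AEs per drug-days at 30 and 42 days after drug initiation (8.2.2.1).

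- All 12 on drug to day 30: 12 × 30 = 360 drug-days; 1000/360 = 2.8 per 1000 drug-days.
- All 12 on drug to day 42: 12 × 42 = 504 drug-days; 1000/504 = 2.0 per 1000 drug-days.
- Assumption, 4 of 12 stop at day 14: 8 × 42 + 4 × 14 = 392 drug-days by day 42; 1000/392 = 2.6 per 1000 drug-days.

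No day-14 figure is given. The first on-drug draw is at week 2 with a window of 2 days either way (Table 5), so it may come after day 14.

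**Relative effect.** If the true number of hematologic events is k and one is omitted, the class rate falls by 1/k. For assumed values of k = 2, 3 and 4 this is 50%, 33% and 25%. These figures show how sensitive a small count is. They do not estimate how many events would be missed.

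**The case against.** The strongest reply is that 7.1.2 does not forbid recording. Its exclusion refers back to the instruction to record a clinically significant result as a single diagnosis. It lifts a requirement, and an investigator following 7.1.1 could still record a symptom-free low count. Section 8.2.2.1 analyses AEs without citing 7.1.2. This stands: omission is possible, not certain. The inconsistent wording is what leaves it open.

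A reader might infer that even severe falls in counts would vanish from the safety results. The documents do not support that. A result judged medically significant is an SAE, and 7.1.2 then makes it an AE as well. Section 1.1.4.3 calls Grade 4 hematologic values medically serious whether or not they meet a set definition, and deep falls would probably be acted on. The realistic gap is mild or moderate symptom-free change.

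A reader might also use the pediatric oncology counts in Table 1 to size the undercount. Sections 1.1.4 and 1.1.4.3 themselves say that those findings cannot be extrapolated, or are unlikely to translate, to this population.

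Finally, this is an uncontrolled pilot in 12 participants with no decision rule, and the original laboratory reports are kept as source documents (11.1), so a summary could be made later. That limits the weight of the point. A summary chosen after the results are known is still weaker than one planned beforehand.

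**Conclusion.** The point holds in a limited form. Sections 5.3.1, 7.1.1 and 7.1.2 do not agree on when a laboratory result is an AE. An AE-only analysis passes that disagreement straight into the hematologic class and, for events judged related, into the primary endpoint. The class may be undercounted; any omission under 7.1.2 lowers it. The documents give no basis for estimating by how much. The per-event figures assume full follow-up or the stated early stopping, and the percentage reductions assume the true counts.

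The effect is on how safety is described. No test or decision rule depends on it, and the blood counts are measured either way, so the gap lies in recording and reporting. It should be corrected, but it does not undermine the design.

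**What to change.** 1. Add to 8.2.2.1, for all treated participants, a by-visit summary of the scheduled hematology and chemistry results: worst post-baseline value, shift from the V1 baseline (the only scheduled pre-dose draw in Table 5), and value-based grade on one named CTCAE version. Report it beside the AE rates, whether or not a result was recorded as an AE.
2. Make the laboratory-AE wording in 5.3.1, 7.1.1 and 7.1.2 consistent, so that one rule decides what is recorded.
3. Separately, 7.1.2 gives interruption as an example of a change in study medication, while 6.2.3 rules out temporary interruptions for safety reasons. The two passages must be reconciled. This does not affect the count discussed here.

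Cost: the tables and the wording edits, plus entry of the numeric results if that is not already planned. Section 9 describes transcription of visit data from clinic notes, and 11.1 lists laboratory reports as source documents; neither says that every value is entered. With 12 participants and five scheduled draws (V1, V3, V4, EOT, SFU) this is 12 × 5 = 60 scheduled sets of results. No extra blood draws or visits are needed. Reported hematologic toxicity may look less favourable.

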The second metric reviewed was SAEs. The incidence of SAEs as reported for the adult VOR studies was 7%; 5% for the pediatric VOR studies, 0.8-10% for VPA studies, and 4.7-8.2% for AEDs. Given the differences in study designs and populations, the rates of SAEs are comparable. The most common SAEs reported in the adult VOR studies were thromboembolic events and anemia; in the pediatric VOR studies, SAEs consisted of thromboembolic events, bleeding/hemorrhage, neuropathy, and hypoxic/acute respiratory distress. Indeed the product monograph indicates that thromboembolic events maybe associated with VOR therapy with an overall incidence rate of 6.8%. However in the pediatric VOR studies, all SAEs were not considered to be related to VOR. Typically however, severity of events in cancer trials are graded using the National Institutes of Health CTCAE Grading system, whereas clinical trials typically utilize the International Council for Harmonisation of Technical Requirements for Pharmaceuticals for Human Use (ICH)/ Good Clinical Practice Guidelines (GCP) for rating severity of events. Utilizing the ICH-GCP definitions, a "serious" AE includes events that are life-threatening. Events rated as Grade 4 using the CTCAE system are considered to be life-threatening. Given this, Grade 4 events using the CTCAE reporting could be considered to be "SAEs". An analysis could not be carried out on the adult VOR studies because Grade 3 and 4 events were grouped together for reporting, however in the pediatric VOR studies, inclusion of the Grade 4 as SAEs caused the incidence rate of SAEs to jump to 65%, with again the most commonly reported events comprising hematologic events and nausea. Although this is an important consideration, it is also important to note that the term 'life-threatening' in the ICH/GCP definition of an SAE refers to an event in which the patient was at risk of death at the time of the event; it does not refer to an event which hypothetically might have caused death if it were more severe. It is not absolutely clear whether these Grade 4 events meet the ICH/GCP criteria for a serious event. However, the fact remains that Grade 4 hematologic events, which according to the CTCAE are platelets $< 25 \times 10^9/\text{L}$; absolute neutrophil count $< 0.5 \times 10^9/\text{L}$; and lymphocyte count $< 0.2 \times 10^9/\text{L}$; are medically quite serious, regardless of whether they meet a pre-set definition. As discussed in the above section, it is unlikely that the rates of incidence found in the Phase 1 VOR pediatric studies are expected in an overall medically stable population; it is anticipated that incidence of SAEs in the proposed population will be that typically seen with VPA/AEDs. However potentially serious hematologic events cannot be ruled out and hematologic testing, in addition to other lab safety testing will be conducted every 2 weeks to monitor study patients. Patients will also be advised of signs of symptoms associated with these hematologic events and to contact the study team in the event of these signs and symptoms. Regarding the other events cautioned to require special monitoring in

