5.3 SAFETY MONITORING

5.3.1 ADVERSE EVENTS

AEs (serious and non-serious) reported by the participant or observed by the investigator will be collected throughout the study. At each visit, the investigator will ask the participant if any untoward medical event occurred since the last visit. For each event, the date of onset and date of resolution, intensity, relationship to study medication, outcome and treatments administered for the event will be recorded in the study record.

AEs will include any symptom, sign, illness or experience, or clinically relevant lab abnormality, regardless of causality, which develops or worsens in severity during the course of the study. An SAE will comprise of any AE, occurring at any dose, regardless of causality that was either life-threatening, requires inpatient hospitalization or prolonging an existing hospitalization, or is determined as an important medical event by the treating physician, or results in death.

All AEs will be reported as stipulated in [Section 7.1](#). SAEs will be reported to the research ethics board (REB) and to Health Canada.

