7.1 ADVERSE EVENTS AND LABORATORY ABNORMALITIES

7.1.1 CLINICAL ADVERSE EVENTS

An AE is any untoward medical occurrence in a patient or clinical investigation participant, administered a pharmaceutical product, which does not necessarily have a causal relationship with the treatment. An AE can therefore be any unfavorable and unintended sign including an abnormal laboratory finding, symptom, or disease temporally associated with the use of a medicinal investigational product, whether or not considered related to the medicinal investigational product. Pre-existing conditions which worsen during a study are also to be reported as AEs.

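### Section 7.1.2 lets a symptom-free low blood count enter the AE data according to how it was handled, not how low it was

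*Combined protocol and SAP*

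**What the plan says.** The general definition in section 7.1.1 is wide: "An AE can therefore be any unfavorable and unintended sign including an abnormal laboratory finding". Section 5.3.1 is somewhat narrower: "AEs will include any symptom, sign, illness or experience, or clinically relevant lab abnormality, regardless of causality".

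Section 7.1.2 then gives the specific rule for laboratory results. A result that fulfils the SAE criteria is reported as an SAE and also recorded as an AE. Any other result is recorded only if it comes with symptoms, leads to a change in study medication, or requires a change in concomitant therapy. The section closes with the exclusion: "This will not apply to any abnormal laboratory result which falls outside the laboratory reference range but which does not meet the clinical significance criteria". It names no grade and no value.

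One SAE criterion in section 7.1.1.3 is that the event "is medically significant or requires intervention to prevent one or other of the outcomes listed above". On stopping, section 7.1.3 says: "Study drug will be discontinued in the presence of an SAE that is deemed to be related or possibly related". It also stops the drug for thromboembolic events, intolerable events, a rise of 50% or more in seizure frequency, and status epilepticus. It lists no blood-count value. For "medically significant unexplained abnormal laboratory test values, the tests will be repeated and followed up", details go into the study record. Under Hematologic Disturbances, section 7.1.3.1 provides scheduled monitoring and asks families to report signs of bleeding or bruising, again without a count limit.

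The recorded AEs supply the primary endpoint (section 8.1.1: related AEs and SAEs, and discontinuations) and the hematologic stratum (section 8.2.2.1).

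**The concern.** Section 1.1.4.3 expects that hematologic events may make up a larger share of AEs than with other anti-epileptic drugs. It is the toxicity this pilot most needs to count consistently. Under section 7.1.2, a low count with no symptoms, no SAE label and no change in treatment is not an AE, however low it is. The same count in another child is an AE if that child's drug was stopped or another medicine was changed. The hematologic rate then reflects partly how investigators responded and only partly what the drug did to the blood count. The laboratory value is not lost, because it stays in the source data. It is the planned safety analysis that misses it.

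**Working it through.** **1. Routes into the AE data for a symptom-free count**

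- *Grade 4.* Section 1.1.4.3 gives the cut-offs as platelets below 25, ANC below 0.5 and lymphocytes below 0.2 (all x10^9/L), and says such counts "are medically quite serious, regardless of whether they meet a pre-set definition". That fits the medically significant criterion in section 7.1.1.3. The relatedness guidance in section 7.1.1.2 (timing, known response pattern) points to related, and section 7.1.3 then stops the drug. So a Grade 4 count is probably recorded and acted on, but each step is the investigator's judgement.
- *Grade 3.* Nothing in the protocol calls a symptom-free Grade 3 count medically significant. The remaining routes need an action. Section 6.2.3 bars temporary interruption for safety, so the only safety-related drug change described is a permanent stop, and no count limit requires one. Unless somebody acts, the result falls under the exclusion.
- *Other provisions.* The repeat rule in section 7.1.3 covers unexplained values, and a fall attributed to vorinostat is arguably explained. Section 5.1.3 allows earlier contact and section 4.7 allows withdrawal. None of these by itself requires an AE entry. The intensity scale in section 7.1.1.1 rests on daily activity, so it does not register how low a count is.

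**2. Check that Table 1 (section 1.1.3) reproduces the protocol's own figures**

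- Thrombocytopenia, Grade 3-4: (16 + 16)/110 = 29.1%, as stated.
- Lymphopenia, Grade 3-4: (19 + 19)/110 = 34.5%, as stated.

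**3. Where a recording limit would have to sit**

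Platelet, neutrophil and lymphocyte lines of Table 1, including the separate ANC line:

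- Grade 3: 16 + 10 + 19 + 1 = 46
- Grade 4: 16 + 2 + 19 + 0 = 37
- Total: 83, of which Grade 3 is 46/83 = 55% and Grade 4 is 37/83 = 45%

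Adding the leukopenia, anemia and hemoglobin lines (Grade 3: 23 + 13 + 1 = 37; Grade 4: 9 + 1 + 1 = 11) makes Grade 3 (46 + 37)/(83 + 48) = 83/131 = 63%. A Grade 4-only limit would therefore leave more than half of such events under the present exclusion. These were pretreated oncology patients, so the split informs the choice of limit and predicts nothing about rates here.

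**4. Weight of one omitted child (N = 12, section 3.3)**

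- As a proportion: 0/12 = 0%, exact 95% upper limit 1 - 0.025^(1/12) = 26.5%. 1/12 = 8.3%, exact 95% CI 0.2 to 38.5%.
- On the planned scale (events per drug-days), assuming all complete: to day 42, 12 x 42 = 504 drug-days, and 100/504 = 0.20 per 100. To day 14, 12 x 14 = 168 drug-days, and 100/168 = 0.60 per 100.

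**The case against.** The strongest reply is that the dangerous counts are already covered. A platelet count below 25 x10^9/L is naturally a medically significant SAE. It would be judged related, because section 7.1.3.1 itself says the drug has dose-related hematologic effects, and it would stop treatment. This largely stands. A reader might infer that Grade 4 counts would go unrecorded while dosing continued. The documents do not support that.

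It is tempting to cite section 1.1.4.3 in support of that inference: "It is not absolutely clear whether these Grade 4 events meet the ICH/GCP criteria for a serious event". But that sentence follows a discussion of the life-threatening criterion and concerns events in past oncology trials. It does not address the medically significant criterion. Nor is hematologic follow-up limited to blood draws, since families are told which symptoms to report.

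A second reply is that the size shown is simply the weight of one child in 12, and would be the same for any misclassified event. That is true. It shows how much one handling decision can move the result and gives no estimate of frequency. A reader might also note that one more SAE takes 1/12 (8.3%) to 2/12 (16.7%), past the 10% in section 5.2.1. That figure is an expectation with no decision attached, so crossing it has no stated consequence.

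Thirdly, relying on investigator judgement is a legitimate choice in a small six-week pilot. That is reasonable for stopping. It is a weaker defence for recording, where the aim is to count like events alike.

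**Conclusion.** The point holds as a recording gap. The exclusion in section 7.1.2 is narrower than the AE definitions in sections 7.1.1 and 5.3.1, and it makes the hematologic stratum depend on how a count was handled. Symptom-free Grade 3 counts are the clearer loss. Grade 4 counts probably enter as SAEs, but by judgement and not by rule. The conclusion assumes that sites follow section 7.1.2 as the specific laboratory rule where it conflicts with the broader definitions.

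No frequency is claimed. Applying the Table 1 rates to 12 children would give the chance of a severe count, not of an unrecorded one, and section 1.1.4.3 argues that the oncology rates are unlikely to carry over. What can be said is that each omitted child moves the proportion with a hematologic event by 8.3 percentage points, or the six-week rate by 0.20 per 100 drug-days if all 12 complete treatment. A change to section 7.1.2 is worth making. A numeric stop is a matter for the sponsor.

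**What to change.** **Recording (section 7.1.2).** Add a fourth condition: *Any post-dose hematology value of Grade 3 or higher on the CTCAE cited in this protocol (platelets, ANC, lymphocytes, white cells, hemoglobin) is recorded as an AE and counted under hematologic disturbances, whatever symptoms or action follow.* The protocol prints only the Grade 4 cut-offs for platelets, ANC and lymphocytes, so the Grade 3 limits should be written out from the cited CTCAE.

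**Stopping (section 7.1.3), optional.** If the sponsor wants a numeric stop: *Platelets <25 x10^9/L or ANC <0.5 x10^9/L are treated as medically significant SAEs; if related or possibly related, study drug is stopped on the first result, without waiting for the repeat.* The stop should not wait for a confirming repeat. Section 6.2.3 bars holds, so dosing would continue meanwhile, and the sentence could be read as weaker than the related-SAE stop already in section 7.1.3.

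**Cost.** The recording change is one sentence. It needs no new scheduled tests, because blood counts are already taken at weeks 2, 4, 6 and 12 (Table 5); this assumes they are reported with a differential. The hematologic AE count may rise. Under the optional stop, a stopped child is not replaced (section 4.8), and a spurious low value could end treatment because section 7.1.3 bars reinstatement. Among scheduled counts, that stop could act only at weeks 2 and 4, since week 6 is the end of treatment.
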